#### **3.3. Design**

The purpose of this study is to evaluate the safety and effectiveness of the Spatz3 in subjects with a BMI  $\geq 30$  and  $< 40$  who have failed to achieve and maintain weight-loss with a weight control program.

Subjects will be studied in a randomized, controlled, multi-center study. The control group will receive dietary/exercise counseling for 32 weeks. The treatment group will receive dietary/exercise counseling plus the Spatz3 balloon for 32 weeks.

The study will run 32 weeks for the control group and 32 weeks followed by a 24-week follow up period for the treatment group.

282 eligible subjects will be randomized to treatment (188 subjects) or control (94 subjects) arms. All treatment group subjects will undergo endoscopy and those without endoscopic contraindications will be implanted with the Spatz3 balloon for 32 weeks. All subjects will follow a 1000-1200 kcal/day-deficit diet during their participation in the study.

At 18 weeks  $\pm$  4 weeks, treatment arm subjects will be evaluated, and those that meet the criteria described below in section 4.3.3.2.4 will undergo an adjustment procedure wherein the balloon volume will be increased to achieve extra weight loss. The balloon adjustment procedure is done with an endoscopy procedure under the same sedation as the implantation procedure. At the end of the 32-week treatment period the control subjects will be dismissed and the treatment group will be explanted and will have a 24-week follow up.

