### **6.4. Protocol Deviations**

All protocol deviations will be documented with the subject number and date of the protocol deviation. The following information will be documented for each protocol deviation:

- Inclusion/Exclusion exceptions or violations, including subject did not sign informed consent prior to study admission
- Follow-up visit not performed or Follow-up outside of window
- Required testing or questionnaire not performed
- Other (Describe)

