## 7. STATISTICS

### 7.1. Description of Statistical Methods

#### 7.1.1. Study cohorts for analyses

The primary analysis will be based on the intent-to-treat dataset, which will include all randomized subjects according to their randomized treatment. However, any subject with an absolute contraindication to balloon implantation which was only revealed at the endoscopy procedure, and who therefore did not receive a balloon, will not be considered in analysis of efficacy.

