The second primary endpoint will be analyzed using the same five imputed datasets created for testing the first primary endpoint, but only the data from subjects in the active treatment group. The estimated proportion of subjects with a  $\geq 5\%$  weight loss at Week 32, along with their associated variance, from each dataset will then be combined using Rubin's method to estimate the overall proportion and its variance. This proportion and its variance will then be used to estimate the one-sided lower 97.5% confidence bound on the proportion of subjects with a  $\geq 5\%$  weight loss at Week 32. If this lower confidence bound exceeds 0.50 the second primary hypothesis will be rejected, and the Spatz3 will be deemed to have met its second primary hypothesis.

As a sensitivity analysis of each co-primary endpoint, an LOCF imputation procedure will be employed in which all missing data among subjects with at least one post-randomization body weight measurement are replaced by the last non-missing value.

Secondary analyses of the primary endpoints will be per protocol and will include subjects according to the actual treatment received and will exclude subjects who did not meet the inclusion criterion of baseline BMI  $\geq 30 \text{ kg/m}^2$  and  $< 40 \text{ kg/m}^2$ .

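### The secondary 'per protocol' analysis is defined as-treated, so some Spatz3-randomized subjects who never get a balloon would, read literally, be counted as controls

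*Combined protocol and SAP*

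**What the plan says.** The primary analysis set in Section 7.1.1 is intent-to-treat, "which will include all randomized subjects according to their randomized treatment". It has one exception: a subject with an absolute contraindication revealed only at endoscopy, "who therefore did not receive a balloon, will not be considered in analysis of efficacy".

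Section 7.1.2 then sets out the supportive analyses of the primary endpoints. It calls them per protocol and says that they "will include subjects according to the actual treatment received and will exclude subjects who did not meet the inclusion criterion of baseline BMI" of 30 to below 40 kg/m². That BMI rule is the only exclusion. The definition does not mention implantation, time with the balloon, adherence or protocol deviations.

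Two other places bear on the reading. Section 3.3 describes the arms: "The treatment group will receive dietary/exercise counseling plus the Spatz3 balloon for 32 weeks". Control subjects get the counselling alone. Section 6.4 requires a record of deviations, among them "Inclusion/Exclusion exceptions or violations, including subject did not sign informed consent prior to study admission", but Section 7.1.2 does not use that record to define the per-protocol set.

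**The concern.** A per-protocol set is normally a subset of each randomized arm, limited to subjects treated as planned. Section 7.1.2 instead sorts subjects by treatment received and removes only those with an out-of-range BMI. A Spatz3 subject who declines on the day, withdraws before placement, or has a failed placement without replacement has been offered counselling only, which is the control regimen. The literal rule puts that subject with the controls.

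Such subjects are self-selected, and many may have little follow-up. Moving them changes both means: the Spatz3 mean loses probable poor performers and the control mean gains them. A supportive analysis should show whether the primary result survives a change of analysis set. Here, part of any change in the estimate could come from the reassignment itself. The set also keeps subjects who breach every eligibility rule other than BMI, so it does not isolate subjects treated according to the protocol.

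Section 7.1.4 already accepts the principle. It warns that comparing subjects with and without a volume change needs caution because the change is not randomized. The same holds for whether a balloon was placed.

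**Working it through.** **The plan's own figure.** Inputs from Section 7.2: means 10.34% and 3.3%, SD 6.6%, margin 4.5%, one-sided 2.5%, 80% power, 2:1 allocation. The effect beyond the margin is 10.34 − 3.3 − 4.5 = 2.54. The control-arm size is (1 + 1/2) × (1.960 + 0.842)² × 6.6² / 2.54² = 79.5, so 80 controls and 160 Spatz3 subjects, 240 in all, as stated. Dropout: 240 / 0.85 = 282.4, against 282 stated. The sample size does not depend on the point at issue.

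**Who could be moved.** Subjects learn their arm on the day of implantation (Section 4.3.2). They may withdraw at any time (Section 4.4). A failed device is replaced unless that is not in the patient's best interest (Section 4.3.3.2.7). Subjects with an absolute contraindication found at endoscopy are already out of all efficacy analyses (Section 7.1.1). That leaves same-day refusals, withdrawals and failed placements. The documents give no count, so the number m is an assumption.

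**Size of the effect.** Take 188 and 94 subjects, means of 10.34% for implanted subjects and 3.3% for controls, and let the m non-implanted subjects have mean %TBL x.

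- By randomized arm: [(188 − m) × 10.34 + m × x] / 188 − 3.3
- Excluded: 10.34 − 3.3 = 7.04
- Moved to control: 10.34 − [94 × 3.3 + m × x] / (94 + m)

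For m = 9, x = 0:

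- By arm: 179 × 10.34 / 188 − 3.3 = 9.845 − 3.3 = 6.545, shown as 6.54
- Moved: 10.34 − 310.2 / 103 = 10.34 − 3.01 = 7.33

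| m (share of 188) | x | By arm | Excluded | Moved |
|---|---|---|---|---|
| 2 (1.1%) | 0 | 6.93 | 7.04 | 7.11 |
| 5 (2.7%) | 0 | 6.76 | 7.04 | 7.21 |
| 9 (4.8%) | 0 | 6.54 | 7.04 | 7.33 |
| 19 (10.1%) | 0 | 6.00 | 7.04 | 7.59 |
| 2 (1.1%) | 3.3 | 6.97 | 7.04 | 7.04 |
| 5 (2.7%) | 3.3 | 6.85 | 7.04 | 7.04 |
| 9 (4.8%) | 3.3 | 6.70 | 7.04 | 7.04 |
| 19 (10.1%) | 3.3 | 6.33 | 7.04 | 7.04 |

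At m = 9, x = 0, moving adds about 0.78 points over the by-arm result. About 0.50 of that comes from taking the subjects out of the Spatz3 arm, and 0.29 from adding them to control.

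**Direction.** Against exclusion, moving favours the device only when x is below 3.3. Against the by-arm result at m = 9, the two are equal when (10.34 − x) / 188 = (x − 3.3) / 103, that is x = (103 × 10.34 + 188 × 3.3) / 291 = 5.8. Imputation matters here. The model includes treatment group, and the plan does not say whether it would be refitted by treatment received. If these subjects were imputed as Spatz3 subjects and then analysed as controls, x could approach 10.34. At that extreme, moving gives 10.34 − (310.2 + 93.06) / 103 = 6.42, below the 7.04 of the other two approaches.

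**Second co-primary endpoint.** This is a Spatz3-arm proportion against 50%, so there is no between-arm comparison to break. The rule only changes the denominator. With m = 9 and none of them responders, the proportion is multiplied by 188 / 179 = 1.05.

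**The case against.** The strongest case on the other side has five parts.

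- **The plan never states the move.** A reader might infer an explicit rule sending every never-implanted subject to control. There is none. Subjects with an absolute contraindication found at endoscopy are dropped, and this is the route to non-implantation that the protocol itself foresees. A subject who withdraws on the day has not had the 32-week control programme either, and could be placed in neither group. This stands. The move is a literal consequence of the wording, limited to the remaining subjects.
- **The bias need not favour the device.** A reader might infer that it always does. The working shows no effect relative to exclusion at x = 3.3 and a reversal above it. This stands.
- **The primary result is not at risk.** A reader might infer that it loses its only check. The primary analysis is by randomized arm, no success rule uses the per-protocol result, and Section 7.1.2 has a separate last-observation-carried-forward sensitivity analysis for each co-primary endpoint. This stands.
- **Excluding the never-implanted also departs from randomization.** It keeps about 0.50 of the 0.78 points in the m = 9, x = 0 case. This is true, and is why any such set is supportive only. Exclusion still avoids adding Spatz3-randomized subjects to the control mean.
- **Removing every eligibility violation would go too far.** Section 6.4 does not grade deviations, and many criteria have little bearing on weight. This stands; a pre-listed set of major deviations is enough.

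None of this removes the core: the stated rule is as-treated, its label is per-protocol, and the handling of non-implanted subjects is left open.

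**Conclusion.** The point holds for the supportive analysis of the first co-primary endpoint. As defined, that analysis does not preserve the randomized comparison and does not select protocol-adherent subjects.

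On the planning means, with 9 of 188 assumed not implanted and losing 0%, reassignment gives 7.33 points, against 7.04 with exclusion and 6.54 by randomized arm. Across the assumed 1% to 10% not implanted and a loss of 0% to 3.3%, it adds about 0.1 to 1.6 points over the by-arm result and 0 to 0.55 over exclusion. For scale, the plan expects to clear its margin by 2.54 points. The number not implanted and their weight loss are assumptions. The probable direction is towards the device, because non-implanted subjects are likely to lose little, but the documents do not establish it.

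This is worth correcting before analysis. It gives no reason to doubt the primary analysis or the sample size.

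**What to change.** In Section 7.1.2, define the per-protocol set as subjects analysed in their randomized arm. Exclude Spatz3 subjects who were never implanted, with no reassignment to control, and subjects with major eligibility deviations. List the qualifying deviations before the data are analysed and take them from the Section 6.4 record. State which treatment label is used when missing weights are imputed for this set.

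If an analysis by treatment received is also wanted, call it as-treated, report it separately, and say where a non-implanted subject is counted.

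The cost is a wording change and a slightly smaller set. No visits, data items or sample size change. The revised set still removes some subjects after randomization, so it should remain supportive only.

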### **7.1.3. Secondary endpoints**

The observed rate of subjects who maintain 40% of the weight loss with the balloon at six months will be compared to a performance goal of 50%.

Percent change in excess weight loss (%EWL) will be calculated by first calculating the excess weight based on a BMI of  $25 \text{ kg/m}^2$ . This endpoint will be analyzed by averaging the mean 32-week changes in body weight for each subject across the five imputations described for the primary endpoint to determine which subjects had a clinical response of a  $\geq 25\%$  loss in excess body weight. This response rate will be compared to a performance goal of 35%.

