## 2. INTRODUCTION

### 2.1. Background

Obesity in the United States has been increasingly cited as a major health issue in recent decades. Like the U.S., many industrialized countries have experienced similar increases, underscoring the severity of the problem. The United States had the highest rate of obesity for large countries (> 32%), until obesity rates in Mexico surpassed that of the United States in 2013[1]. Childhood obesity has more than doubled in children and quadrupled in adolescents in the past 30 years [1].

The American Heart Association (AHA) notes that 60-70% of the US population is either overweight or obese, putting them at risk for heart disease, stroke, high blood pressure and diabetes. According to the AHA, obesity affects nearly 78 million adults and 13 million children in the US today. The CDC found there was no decrease in obesity rate from the 2009-2010 survey to the 2011-2012 survey [3].

Among Americans age 20 and older, 154.7 million are overweight or obese (BMI of 25.0 kg/m^2 and higher): - 79.9 million men and 74.8 million women. Of these 154.7 M, 78.4 million are obese (BMI of 30.0 kg/m^2 and higher): 36.8 million men and 41.6 million women. If current trends in the growth of obesity continue, total healthcare costs attributable to obesity could reach \$861 to \$957 billion by 2030, which would account for 16% to 18% of US health expenditures (AHA) [3].

To date, treatment options for the US obese population include weight loss management programs, pharmaceuticals, and bariatric surgeries (gastric bypass, sleeve gastrectomy and gastric banding accounting for 99% of the bariatric surgeries) [4]. FDA has also recently approved the Enteromedics vagal nerve stimulator and the Orbera intragastric balloon and the Reshape Duo intragastric balloon, but it is too soon to assess the potential impact of these therapies.

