#### **3.2. Endpoints**

##### **3.2.1. Effectiveness**

There are two co-primary effectiveness endpoints:

- Percent change in total body weight (%TBL) at 32 weeks; and
- Clinical response, where a responder is defined as a subject with at least a 5% loss in total body weight at 32 weeks

There are two secondary endpoints:

- Maintenance of 40% of the total body weight loss with the balloon six months after the balloon is removed
- Clinical response, where a responder is defined as a subject with at least a 25% loss in excess body weight at 32 weeks

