23. Patients who have ever developed a serotonin syndrome and are currently taking any drug known to affect the levels of serotonin in the body [e.g., selective serotonin reuptake inhibitors (SSRIs), serotonin-norepinephrine reuptake inhibitors (SNRIs), monoamine oxidase inhibitors (MAOIs)] should not undergo placement of the device.
24. Patients who are pregnant or breast-feeding.

25. Subjects with Severe cardiopulmonary disease or other serious organic disease which might include known history of coronary artery disease, Myocardial infarction within the past 6 months, poorly-controlled hypertension, required use of NSAIDs
26. Subjects who have tested positive for H. Pylori.
27. Subjects taking medications on specified hourly intervals that may be affected by changes to gastric emptying, such as anti-seizure or anti-arrhythmic medications
28. Subjects who are taking corticosteroids, immunosuppressants, and narcotics
29. Subjects who are taking diet pills
30. Use of an intragastric device prior to this study due to the potential increase in risk associated with implantation of a balloon in a previously instrumented and possibly scarred stomach.
31. Participation in any clinical study which could affect weight loss within the past 6 months due to the potential to confound findings.
32. Symptomatic congestive heart failure, cardiac arrhythmia or unstable coronary artery disease.
33. Pre-existing respiratory disease such as chronic obstructive pulmonary disease (COPD), pneumonia or cancer.
34. Diagnosis of autoimmune connective tissue disorder (e.g. lupus, erythematous, scleroderma) or immunocompromised.
35. Life expectancy less than 1 year or severe renal, hepatic, pulmonary or other medical condition, in the opinion of the investigator because of an increased risk profile.
36. Specific diagnosed genetic or hormonal cause for obesity such as hypothyroidism or Prader Willi syndrome
37. Eating disorders including night eating syndrome (NES), bulimia, binge eating disorder, or compulsive overeating
38. Known history of endocrine disorders affecting weight

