#### 4.3.4. Follow-Up Schedule

Follow-up visits for treatment and control patients will occur according to the following schedule: Visits at 1 week, 2 weeks, and 4 weeks ( $\pm$  3 days), and thereafter every 4 weeks ( $\pm$  2 weeks) until primary endpoint assessment at 32 weeks. In addition, 1-2 weeks after the adjustment procedure the subject will have a follow up appointment with the PI/NP.

Each follow-up visit will include:

1. Clinical assessment by PI or nurse practitioner or physician’s assistant for both the treatment group and control group (*Appendix E6: CRF6\_Control Group PI Follow Up* or *Appendix E7: CRF7\_Treatment Group PI Follow Up*)
2. Satiety and Dietary Assessment for both the treatment group and control group - limited to 30-45 minutes per session (*Appendix E8: CRF8\_Control Group Dietician Follow Up* or *Appendix E9: CRF9\_Treatment Group Dietician Follow Up*)
3. Record adverse events, device complications, concomitant medication (*Appendix E6: CRF6\_Control Group PI Follow Up* or *Appendix E7: CRF7\_Treatment Group PI Follow Up*)
4. Weight to be done by staff (patient may not speak with weighing personnel and may not disclose if they are control or treatment arm)

Control patients will exit the study at Week 32. Treatment patients will have the device explanted and will be followed for an additional 24 weeks according to the following schedule: Visits at Week 36 ( $\pm$  3 days) and thereafter every 4 weeks ( $\pm$  2 weeks) until 56 weeks. Treatment patients who undergo balloon extraction prior to 32 weeks will be followed from the time of balloon extraction an additional 24 weeks according to the following schedule: Visits at 4 Weeks post extraction ( $\pm$  3 days) and thereafter every 4 weeks ( $\pm$  2 weeks) until 24 weeks after the extraction.

These follow-up visits for the treatment group only, will include:

1. Clinical Assessment - only at the visit 4 weeks post extraction(*Appendix E7: CRF7\_Treatment Group PI Follow Up*)
2. Satiety and Dietary Assessment (*Appendix E9: CRF9\_Treatment Group Dietician Follow Up*)

A summary of required visits and procedures for subjects who do not require an unscheduled endoscopy is shown in the following table and provided in *Appendix B: Study Visits and Master Schedule*:

Assessment / Procedure	Screening Assessments	7 Days Prior to implant	Implantation	Adjustment	Explantation	Follow-Up Assessment weeks 1-32	WEEKS 36 - 56
Informed Consent	X						
Date of birth/gender	X						

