Body Weight	X	X	X	X	X	X	X
Body Height	X						
BMI	X	X	X			X* (week 32)	X * (week 56, or 24 weeks after extraction)
Ideal weight/ Excess Weight	X				X	X* (week 32)	X * (week 56, or 24 weeks

Assessment / Procedure	Screening Assessments	7 Days Prior to implant	Implantation	Adjustment	Explantation	Follow-Up Assessment weeks 1-32	WEEKS 36 - 56
							after extraction)
Medical History	X						
Physical Exam 	X			X	X		Week 36, or 4 weeks after extraction
Blood Pressure	x		X	X	X	X	Week 36, or 4 weeks after extraction
CBC  Coag  (Coag @ screen only)	X						Week 36, or 4 weeks after extraction
H. Pylori Serology	X						
Chemistry Panel 	X						X Week 36, or 4 weeks after extraction
HgbA1C2 IF DIABETIC	X						X Week 36, or 4 weeks after extraction
EKG*(Females and Males >40 y/o	X						
Psychological Evaluation	X						
Inclusion and Exclusion Criteria	X						
Develop/Review Dietary Plan	X						
Satiety and Dietary Assessment						X	X (or 24 weeks after extraction)
Investigator or Nurse follow up				X	X	X	X (or 24 weeks after extraction)
Medications List	X	X				X	X Week 36, or 4 weeks

 Investigator or co-investigator must perform physical exam.

 See section 4.3.1 for required tests

Assessment / Procedure	Screening Assessments	7 Days Prior to implant	Implantation	Adjustment	Explantation	Follow-Up Assessment weeks 1-32	WEEKS 36 - 56
							after extraction
Urine Pregnancy Test women of child bearing potential*	X	X					
Adverse Events/Device Complications			X	X	X	X	X
Verify Birth Control for Females	X						

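### The weight-only, single-arm maintenance endpoint has no rule for weight-loss treatment started after balloon removal, and such treatment need not be recorded after the first post-removal visit

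*Combined protocol and SAP*

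**What the plan says.** Section 3.2.1 defines the first secondary endpoint as "Maintenance of 40% of the total body weight loss with the balloon six months after the balloon is removed". Section 7.1.3 gives the analysis: "The observed rate of subjects who maintain 40% of the weight loss with the balloon at six months will be compared" with a 50% performance goal. It names no test, confidence bound or denominator, and no handling of other weight-loss treatment. Section 7.1.5 only points back to 7.1.2, whose imputation model uses weights through Week 32.

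Section 4.3.4 sets out what is collected and when:

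- "Control patients will exit the study at Week 32", so only the device arm is followed after that.
- To Week 32, every visit records concomitant medication. The list of post-extraction visit contents does not repeat that item.
- The post-extraction list has "Clinical Assessment - only at the visit 4 weeks post extraction", plus the satiety and dietary assessment.
- In the visit table, the row "Medications List" is marked in the Weeks 36-56 column only for Week 36, or 4 weeks after extraction. Body weight, adverse events, dietary assessment and investigator or nurse follow-up are also marked in that column.

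The diet-pill exclusion (3.5.2 item 29, "Subjects who are taking diet pills") is an entry criterion. Section 3.5 applies the eligibility criteria at randomization. No supplied text restricts weight-loss treatment after extraction.

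**The concern.** The maintenance rate is meant to show that weight lost with the balloon stays off once the balloon is out. A subject who regains, starts another treatment and is back under the threshold at 24 weeks is scored the same as one who kept the weight off unaided. Later treatment is plausible. Inclusion criterion 5 requires a history of failed weight-loss attempts, and sections 2.1 and 2.2 describe drugs, devices and surgery available in the US (for example, "FDA has also recently approved the Enteromedics vagal nerve stimulator and the Orbera intragastric balloon and the Reshape Duo intragastric balloon").

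In a randomized comparison, some of this would occur in both arms. Here the rate stands alone against a fixed number, so effective other treatment can only raise it. If the information is not collected prospectively, the analysis may be unable to tell how much of a rate above 50% reflects the balloon.

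**Working it through.** **1. The plan's own figures.** The maintenance endpoint has no stated sample size, power or alpha. The only calculation, in 7.2, is for the first co-primary endpoint. The difference beyond the margin is 10.34 − 3.3 − 4.5 = 2.54, with SD 6.6, one-sided 2.5%, 80% power and 2:1 allocation. This reproduces 80 controls and 160 device subjects (power 80.2%), and 240/0.85 = 282.4 agrees with the stated 282. I therefore use 160 and 188 as two candidate denominators for maintenance.

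**2. What the schedule covers.** Visits every 4 weeks from Week 36 to Week 56 make (56 − 36)/4 + 1 = 6 visits. The medications review is marked at the first only. The remaining 56 − 36 = 20 weeks, up to the endpoint weight, have none.

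**3. Direction and size.** Let m be the unaided maintenance rate and u the fraction who start effective other treatment and reach the threshold with it. If starters are otherwise typical, the observed rate is m(1 − u) + u.

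- m = 45%, u = 10%: 0.405 + 0.10 = 50.5%
- m = 45%, u = 15%: 0.3825 + 0.15 = 53.25%
- m = 40%, u = 20%: 0.32 + 0.20 = 52%

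The same formula applies if u is read as the share of would-be non-maintainers who are converted. Both m and u are assumptions.

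**4. Does it change the result?** That depends on what the comparison in 7.1.3 means. I took two readings: success if the observed rate exceeds 50%, and success by an exact one-sided 2.5% binomial test (my assumption, borrowing the primary alpha). The exact test needs 93/160 (58.1%) or 108/188 (57.4%). Probabilities of success are for N = 160 / N = 188:

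| m | u | Apparent rate | Observed rate above 50% | Exact 2.5% test |
|---|---|---|---|---|
| 40% | 0 | 40% | 0.4% / 0.2% | under 0.01% |
| 40% | 20% | 52% | 67% / 68% | 7.0% / 7.7% |
| 45% | 0 | 45% | 8.9% / 7.4% | 0.06% / 0.04% |
| 45% | 10% | 50.5% | 51.9% / 52.6% | 3.2% / 3.3% |
| 50% | 0 | 50% | 47% / 47% | 2.4% / 2.4% |
| 50% | 5% | 52.5% | 71% / 73% | 8.9% / 9.9% |
| 50% | 10% | 55% | 88% / 90% | 23.8% / 27.5% |

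To bring the expected count up to the exact-test threshold from m = 50%, 93 − 80 = 13 of 160 (or 108 − 94 = 14 of 188) subjects must be converted. From m = 45% it takes 93 − 72 = 21 of 160 (or 108 − 84.6, about 23, of 188).

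**5. What scoring starters as failures would estimate.** If starters are otherwise typical, the rate becomes m(1 − u). At m = 45% and u = 15% that is 38.25% against 53.25% as observed, and below the unaided 45%. If only would-be regainers start treatment, it equals m. It is therefore a conservative bound, not an estimate of the unaided rate.

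**The case against.** Several points on the other side stand.

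- A reader might infer that the protocol instructs that users of other treatment be counted as maintainers. It does not. They count by default, because the definition makes no exception.
- A reader might infer that the entry exclusions show an intent to credit weight change to the balloon, later abandoned. The text supports this only in part. Item 31 (recent studies) mentions confounding, but item 30 (earlier intragastric devices) cites the risk of a scarred stomach. Diet pills and bariatric surgery carry no stated reason.
- A reader might infer that later treatment could never be discovered. That goes too far. The table marks adverse events and investigator or nurse follow-up to Week 56, section 6.2.3 has subjects questioned about adverse events at each visit, and source documents include medical records (8.2). The case report forms are not supplied. The table's investigator or nurse row also sits uneasily with the text limiting clinical assessment to one visit. Still, incidental discovery is not systematic recording.
- No document gives an uptake, and the formula counts every user as a success. The protocol's own background figures are modest: 3-3.7% weight loss in a year for one drug, and 0.6% penetration for gastric bypass. Under a 2.5% test, moderate uptake rarely rescues a true rate of 45%.
- Using the observed weight whatever treatment follows is a recognized estimand strategy. Scoring all starters as failures also penalizes someone who had kept most of the loss before starting an over-the-counter product.

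These points limit the claim about size and argue against imposing failure scoring as the only analysis. They do not fill the gap in data collection or in the rule.

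**Conclusion.** The concern holds as a gap in definition and data collection. The maintenance rate is weight-only and single-arm, has no rule for weight-loss treatment started after extraction, and is not supported by any required recording of such treatment over the last 20 weeks. Any bias is upward, and its size is unknown.

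It matters mainly in two situations: an unaided rate near 50%, or a comparison that uses the bare point estimate. On the second reading, a 45% unaided rate with 10% assumed uptake passes about 52% of the time instead of 7-9%. Under an exact 2.5% test the same case passes about 3% of the time. The documents do not support the stronger conclusion that the trial is likely to pass its goal because of other treatment. The issue is confined to one secondary endpoint. For early removals, 7.1.2 takes the weight just before explant, so treatment started after extraction does not enter the device arm's 32-week results.

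**What to change.** In the 4.3.4 table and the post-extraction visit list, extend the medications review to every visit from Week 36 to Week 56 (or to 24 weeks after extraction). Add a question on weight-loss drugs, devices and procedures, with start dates.

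In 7.1.3, report the maintenance rate in two ways: as observed, and with subjects who started such treatment after extraction scored as non-maintainers. State in advance which is the main analysis. State also that the second is a conservative bound, m(1 − u) if starters are otherwise typical, and not the unaided rate. The gap between the two rates is the share of subjects who reached the threshold after starting other treatment, which is what a reader needs to judge a result near 50%.

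The cost is one extra question and a medications check at visits already held, plus a short addition to 7.1.3. The second rate may be noticeably lower if uptake is material: 15 points at the assumed 15%.
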